VLC Diet. Participants will be encouraged to eat a VLCD, the same one [name] has found effective in her previous research,[9] and to reduce carbohydrate intake to between 20-35 non-fiber grams of carbohydrates a day with the goal of achieving nutritional ketosis, defined as a positive urine dipstick (Bayer Ketostix), which measures the ketone acetoacetate. A VLCD restricts carbohydrate intake to a point that induces a low level of ketone production. Nutritional ketosis may indicate that insulin levels are reduced to a level that the body is using fat as the key source of energy, turning on fat burning (lipolysis).¹⁵ When this occurs, some fats are turned into ketones, which serve as a readily used fuel.¹⁶ This is a commonly used approach,[10, 11] and results from our pilot[9] and other studies[12-15] provide empirical support for this type of diet.[16]

Support. As changing a diet can be complex, several sessions are necessary to comprehensively and effectively teach a new way of eating. All participants will be e-mailed links every week for 16 weeks that connect them to a) a short survey to assess intervention-related behavioral adherence and health concerns, b) a short video to teach the topics, c) downloadable handouts distributed online to accompany the videos, and d) links to external resources on the web pertaining to the week's information. As some participants prefer not to watch videos, the transcripts of the embedded videos will be provided as well, in an easy-to-read downloadable format. The lessons can be watched and read whenever is convenient and take about 10 to 30 minutes to complete. As coaches have been found to be effective additions to behavioral interventions,[17] if participants in the groups have questions, they will be able to contact a coach in order to receive prompt replies. Coaches will be trained, and coaching quality will be monitored for fidelity to our coaching manual.

All participants will be provided with extra support tools. These will be taught with a weekly short video, downloadable handouts, and links to external resources. Below, we describe the justification for the behavioral support we include.

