c) Body weight self-monitoring using a digital scale. At the start of their 4-month program, participants will be mailed a scale. We will ask participants to track their body weight weekly with this scale, which is easy

to use and connects via a cellular network. Because it connects via its own cell network, participants do not have to set up any passwords, simplifying ease of use. We will use this information to monitor participant success and tailor coaching support.

d) Mailed materials. At week 1, week 6 and week 11, we will mail participants lay-press cookbooks to help with increasing variety in their diet. This approach has been popular with our previous participants. Although meal replacements have been studied, and are generally found to be helpful for weight loss,[31, 32] this cookbook approach is novel. Also at week 1, participants who are taking glucose-lowering medication (other than metformin) will be sent a glucose-monitoring device via Amazon, so that they may self-monitor their glucose.

e) Text messages. Reminders about targeted behaviors are tied to greater behavioral adherence.[33] Thus, to encourage the adoption and maintenance of the new intervention-related behaviors, participants will be sent text messages to give them feedback as well as to motivate, educate, and remind them about the targeted behaviors and skills.[34] Thus, as [name] has done in her previous research, we will send automatic, motivational, and educational skill-relevant messages about 5 times a week to participants.[35, 36] Although most previous participants enjoyed the messages, participants have the option to opt out of text messages.

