Safety and medication management. Participants will be asked in a weekly survey about health symptoms or adverse events they've experienced and to report any medication changes they've made. Participants who report symptoms will be reached by email as soon as possible by the study coordinator or diet coach. Participants may be called if the health event seems urgent or severe. For severe or long lasting symptoms, participants will be encouraged to reach out to their primary care physician. Participants who are taking some blood glucose-lowering medications (metformin, DPP-4s, GLP-1 agonists, and Thiazolidinediones (TZDs)) will continue their medications as normal. Participants taking all other glucose-lowering medications will be asked to stop taking these medications at the start of the trial (PCPs will be informed of this change when participants begin the trial). All participants will be asked in the aforementioned weekly survey about their highest and lowest fasted and postprandial (2 hours after eating) blood glucose levels over the previous week. If participants report low glucose (fasting below 70 mg/dL or postprandial below 110 mg/dL), they should reach out to their physician and follow self-management guidelines (sent to them as part of week 1's intervention materials). If participants report more than two weeks of high blood glucose (180 mg/dL), [name] [name] will reach out to participants via email or phone about management and reach out to participant PCPs.

Outcomes and analyses. After 16 weeks of the VLCD program, participants will complete a series of follow up measurements. Participants will complete a virtual follow up office visit, a follow up self-report survey, track their food, weigh themselves on the scale we sent them, take an at-home urine pregnancy test (if of childbearing potential), and return for a MRI-derived proton density fat fraction test. All final measurements should be completed within 4 weeks of completion of the program. Additionally, the second MRI will be conducted on research machines and charged to the study. Participants will also have a fasting blood draw. Follow up blood tests will include: complete blood count with differential, comprehensive metabolic panel, prothrombin time, fasting glucose, hemoglobin A1c, fasting insulin, and a serum lipid panel.

Statistical Design:

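### No reported high glucose value requires study contact before about the third weekly survey, even for participants the study asked to stop glucose-lowering drugs

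*Combined protocol and SAP*

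**What the plan says.** The relevant text is in the section on safety and medication management. Metformin, DPP-4s, GLP-1 agonists and TZDs continue. Participants on any other glucose-lowering drug "will be asked to stop taking these medications at the start of the trial", and "PCPs will be informed of this change when participants begin the trial". Every week participants are asked "about their highest and lowest fasted and postprandial (2 hours after eating) blood glucose levels over the previous week".

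Two rules act on these values:

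- **Low glucose.** There are separate limits for fasting (70 mg/dL) and postprandial (110 mg/dL) values and no waiting period. The action falls to the participant: "they should reach out to their physician and follow self-management guidelines".
- **High glucose.** The rule begins "If participants report more than two weeks of high blood glucose (180 mg/dL". The study then contacts the participant and the PCP. The rule gives one figure, with no fasted or postprandial label and no second tier.

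The same section has staff email participants who report symptoms, and adds: "Participants may be called if the health event seems urgent or severe". Under Mailed materials, participants on glucose-lowering drugs other than metformin "will be sent a glucose-monitoring device via Amazon" at week 1. Under NAFLD standard of care, study physicians are on call for adverse events. Under Support, a coach answers questions, and "coaching quality will be monitored for fidelity to our coaching manual".

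**The concern.** The study itself withdraws treatment from some participants and collects the value that would show loss of control. It then sets no required response to that value for two full weekly reports. A week in which every fasted reading was above 180 mg/dL is handled in the same way as a week with one postprandial reading of 181.

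The weekly survey is the only glucose surveillance described during the 16 weeks. The study clinic visits and blood draws described are at baseline and after the program. If a participant feels well, nothing in the text makes a high reading lead to contact until the duration condition is met. What is at stake is the speed of a safety response in a subgroup that the protocol creates.

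**Working it through.** **Other routes to contact.** The question for each is whether a high reading, without symptoms, requires the study to act.

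| Route | What sets it off | Required by a high value? |
|---|---|---|
| Email from coordinator or coach | Reported symptoms | No |
| Telephone call | A health event judged urgent or severe; discretionary | No |
| On-call physicians | Adverse event | No glucose value given |
| Coach | Participant's question | No |
| PCP | Told of the stop; later contact left to the patient | No |
| Extra physician attention | Insulin users, only if that exclusion is relaxed | No threshold given |
| High-glucose rule | More than two weeks at 180 mg/dL | Yes |

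**Timing.** The plan states no day for this contact, so there is no figure to reproduce.

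Inputs from the document: 16 weekly surveys (16 × 7 = 112 days), each covering the previous week; a duration of more than two weeks; a meter sent at week 1. Assumptions, because the document does not give them: the first survey falls on day s = 1, 3 or 7 after the drugs are stopped; the meter is usable from day m = 0, 3 or 7; every reading is high.

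Survey k falls on day s + 7(k − 1). It can report a high week only if its day is later than m. I took the rule as met at the third survey that can report. Requiring instead that the survey day minus m exceeds 14 gives the same result in all nine cases.

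| First survey day | Meter day 0 | Meter day 3 | Meter day 7 |
|---|---|---|---|
| 1 | 15 | 22 | 22 |
| 3 | 17 | 24 | 24 |
| 7 | 21 | 21 | 28 |

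For example, with s = 7 and m = 0, the surveys on days 7 and 14 cover exactly 14 days, which is not more than two weeks, so the rule is met on day 21. The range is day 15 (15/112 = 13.4% of the program) to day 28 (28/112 = 25%), and never before the third survey.

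**With a one-survey trigger.** Contact is required at the first survey that can report, which is two survey intervals earlier: 2 × 7 = 14 days in every cell. The range becomes day 1 to day 14. The earliest of these surveys would hold little post-stop data.

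**How often a lowest-fasted trigger would fire.** Assume independent, normally distributed fasted readings with SD 20 mg/dL. The lowest value exceeds 180 only if all n readings do, so the probability is P(reading > 180)^n.

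- Mean 160: P = 0.159. One reading gives 16%, two give 0.159² = 2.5%, three give 0.159³ = 0.4%.
- Mean 220: P = 0.977. Seven readings give 0.977⁷ = 85%.

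**The missing label.** With an assumed highest fasted value of 150 and highest postprandial value of 185 for three weeks, the rule is met if 180 covers postprandial values and not met if it covers fasted values only.

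**The case against.** The strongest reply is that the wait is deliberate. Drugs are stopped while carbohydrate is cut to 20–35 non-fiber grams a day, and the stated reason for stopping them is the risk of hypoglycemia. Some instability is expected, and reacting to single readings could be unhelpful. Fasting glucose, fasting insulin and HbA1c are measured before enrolment, and the PCP must approve participation, so glycemic status is known beforehand. This is a fair defence of keeping the two-week rule for ordinary readings. It does not explain why a wholly high fasted week needs the same wait.

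The reach may also be small. Diabetes is not an inclusion criterion, four drug classes continue, and insulin users are excluded by default. Of 40 participants, the number who stop drugs is not given and could be zero. That stands, and it limits the weight of the point.

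A reader might infer more than the text supports in three ways:

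- **That the study will not, or may not, act before the third survey.** The text does not say so. Staff may call about an event they judge urgent, and neither that route nor the on-call route excludes a very high reading. The coaching manual and the week 1 guidelines are not in the document and may add detail. The gap is in what is required.
- **That the delay is shown to be harmful.** The document has nothing on the effect of 14 more days at such values; that is for the study physicians to judge.
- **That the missing label makes the rule unworkable.** The survey asks for both kinds of value, and the ordinary reading is that either counts. On that reading the participant described here does meet the rule, only late. The label is a clarification and does not carry the point.

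**Conclusion.** The point holds as a gap in the stated safety rule. Applied as written, the plan requires no contact with a symptom-free participant who has stopped drugs and has only high fasted readings until about the third weekly survey. Roughly day 15 to day 28 is the range under the assumed survey days and meter arrival, with weekly surveys completed on schedule; no single day in it should be read as the plan's own. A one-survey trigger would bring required contact forward by 14 days. This is a cheap improvement to patient safety in a subgroup of unknown and possibly very small size. It does not show that the trial is unsafe, and it does not touch the efficacy analysis.

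**What to change.** Leave the existing rule and its duration as they are. Make two changes to the section on safety and medication management:

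1. State that 180 mg/dL applies to either a fasted or a postprandial value.
2. Add one sentence: for participants who stopped glucose-lowering drugs, the study also contacts the participant and the PCP after any single weekly survey in which the lowest fasted value is above 180 mg/dL, or in which any value reaches a higher urgent level set by the study physicians before enrolment.

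The first trigger uses a survey item already collected and the protocol's own figure. The document gives no figure for the urgent level, so the physicians must choose it.

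The cost is a few extra emails or calls. For the lowest-fasted trigger these would come mostly from weeks with only one or two fasted readings, where a single 181 can be enough. The cost of the urgent-level trigger depends on the level chosen.

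I would not define the existing rule as any three surveys out of 16. If 10%, 20% or 30% of weeks contain one value above 180 mg/dL, independently, the binomial chance of three or more such weeks is about 21%, 65% or 90%. That would require contact for scattered isolated readings and would change the rule, not clarify it.

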
[figure not shown]
Participants may be ineligible after their blood tests and virtual visit. If no other cause of elevated liver function tests is found except for NAFLD and the patient meets inclusion with no exclusion criteria, the patient will attend their second appointment at the main Michigan Medicine hospital to receive a baseline standard-of-care, clinical liver MRI-derived proton density fat fraction test, the gold standard for non-invasive measurement of both hepatic steatosis, fibrosis, and cirrhosis. Prior to this appointment, participants of childbearing potential will be mailed a urine pregnancy test. They'll be instructed to take this test the day of their MRI and to send a photo of the result to the study email (they can write their result if they're uncomfortable with a photo).

Participants with a positive test will be asked not to come in for their appointment and will not be eligible for the trial. At the second appointment, participants will complete an MRI screening with the technicians and may be ineligible if they are unfit for an MRI. Those whose MRI shows steatosis, mild fibrosis, and early cirrhosis (F1-4), will be invited into the trial, as these are the patients for whom we may be able to reverse fibrosis with intervention. (See **Figure 1** for the full flowchart of the study.) If participants are ineligible after completing their MRI, they will be compensated \$20 via Amazon gift card. The “psychological self-report” listed in Figure 1 for baseline and 4-month assessments includes questions concerning health-related quality of life,[1] dietary intake, physical activity,[2, 3] food cravings,[4] stress eating,[5, 6] dietary-based social support,[7] and hunger.[8]

Participants who are eligible after their MRI and have completed all other baseline measurements will be mailed a digital scale. Participants must weigh themselves on this scale within two weeks of receipt, before being enrolled in the trial.

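### For participants asked to stop a glucose-lowering drug, the insulin-resistance comparison pairs on-drug with off-drug values, and the visible text states no handover at program end

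*Combined protocol and SAP*

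**What the plan says.** Safety and medication management lets users of metformin, DPP-4s, GLP-1 agonists and TZDs carry on. For the rest: "Participants taking all other glucose-lowering medications will be asked to stop taking these medications at the start of the trial". Primary care providers are told of this when the participant begins. The visible text does not say when the stop ends or who reviews it.

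The same section describes a weekly survey. It asks about symptoms or adverse events "experienced and to report any medication changes", and "about their highest and lowest fasted and postprandial (2 hours after eating) blood glucose levels over the previous week". The outreach rule begins "If participants report more than two weeks of high blood glucose (180 mg/dL" and then has the study contact both the participant and the primary care provider. This section gives the survey no end date. The Support section says: "All participants will be e-mailed links every week for 16 weeks that connect them to a) a short survey", and describes that survey as covering adherence and health concerns.

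Outcomes and analyses places follow-up after the 16 weeks: "Participants will complete a virtual follow up office visit, a follow up self-report survey, track their food", together with weighing, MRI and a fasting draw that includes glucose, HbA1c and insulin. On timing: "All final measurements should be completed within 4 weeks of completion of the program". The psychological self-report "listed in Figure 1 for baseline and 4-month assessments includes questions concerning health-related quality of life", then diet, activity, cravings, stress eating, social support and hunger. No drug item is listed there. Figure 1 itself is not shown.

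Statistical Design makes post-program versus baseline insulin resistance a secondary outcome, tested with a one-sample Wilcoxon test. It does not mention drug changes.

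**The concern.** Two things follow from a drug stop that the study itself requests.

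**Reading the result.** The insulin-resistance test treats each participant's change as the result of the program. For a drug-stopper, the change also contains the withdrawal of a glucose-lowering drug. In a single-arm study there is no comparison group in which that part would cancel. If the drug is restarted after the last weekly survey, the analyst may not know which kind of pair is in hand.

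**Safety.** The provider is informed when the drug is stopped, but no message to the provider is described when the program and its coaching end. If the weekly survey ends at the same time, the one glucose rule under which the study contacts both participant and provider ends with it.

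**Working it through.** **1. The plan's own figure.** No figure in the plan depends on the drug stop. The only calculation is the liver-fat power: loss 12, SD 6, n = 40, α = 0.01. The standardised effect is 12/6 = 2. With the Wilcoxon efficiency 3/π, 2 × √(40 × 3/π) = 2 × √38.2 = 12.4. Subtracting the two-sided critical value 2.58 gives 9.8, so power is about 100%. A noncentral t calculation and a simulated signed-rank test (4,000 runs) give the same. This agrees with the stated 99%, and the present point does not change it.

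**2. Order of events.** The fasting baseline draw is taken within one to two weeks of the first virtual visit. Provider approval, the baseline MRI and home weighing must all be complete before enrollment, and the drug stop comes when the trial starts. The final draw follows week 16. The baseline value is therefore on-drug, and the final value is off-drug unless the drug was restarted.

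**3. Reporting window.** Assume that the two descriptions of a weekly survey refer to one survey. Reports then run to week 16 and final measurements to week 20 at the latest: 20 − 16 = 4, a gap of 0 to 4 weeks depending on when a participant is measured.

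**4. What the analyst would know about each pair.**

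| Participant | Pair | Known from planned data? |
|---|---|---|
| No such drug, or a drug that continues unchanged | Like with like | Yes, through week 16 |
| Stopped, restarted by week 16 | On-drug, on-drug | Yes, from weekly reports |
| Stopped, still off at the final draw | On-drug, off-drug | Through week 16 only |
| Stopped, restarted after the last survey | On-drug, on-drug | Not by any written item |

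The third row is created by the planned stop. The reporting gap only makes it hard to separate the third row from the fourth. A late restart brings the pair closer to like with like.

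**5. Outreach rule.** More than two weeks of high reports means at least three weekly reports. If the first high week is w, the reports available are 16 − w + 1. At least three requires w ≤ 14; week 15 gives two and week 16 gives one. If the items continued to week 20, the limit would be w ≤ 18. If each survey covers the week before it is sent, the limits are 13 and 17. The extension gains four weeks under either reading for someone measured at week 20, and nothing for someone measured at the end of week 16.

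**6. Size of the group.** The documents give no count. For an assumed share p of 40 participants, the expected number is 40p and the chance of at least one is 1 − (1 − p)^40.

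| Assumed p | Expected number | Chance of at least one | Pairs left if all are set aside |
|---|---|---|---|
| 2.5% | 1 | 63.7% | 39 |
| 5% | 2 | 87.1% | 38 |
| 10% | 4 | 98.5% | 36 |
| 15% | 6 | 99.8% | 34 |

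The last column ignores dropout. The shift in the insulin-resistance result cannot be computed: the documents do not name the drugs stopped and give no expected change or SD for insulin resistance.

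**The case against.** The other side has a strong case, and much of it stands.

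- **The week-16 end is inferred.** The safety section sets no end date. Identifying its survey with the e-mailed one is plausible, since no other weekly survey is described, but it is an assumption.
- **Drug status is not simply missing.** The planned stop and the weekly drug-change reports give it through week 16. Only a change in the following 0 to 4 weeks is uncovered. A drug question would be natural at the follow-up visit and may be in Figure 1 or the visit form.
- **Cover continues.** NAFLD standard of care has adverse events queried at each clinic visit and physicians on call. Providers are told that patients may contact them about drug adjustments. Users of glucose-lowering drugs other than metformin are mailed a meter. A glucose and HbA1c draw falls in the same four weeks.
- **Few people are involved.** Four drug groups continue and insulin users are excluded at first. The group could grow if that exclusion is relaxed, but those participants are promised extra physician attention.

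A reader might infer from step 5 that high glucose starting in any of weeks 15 to 20, or 6 of 20 weeks, goes unnoticed, and take 30% as a risk. The documents do not support that. The count applies only to a first high week, because the rule does not require consecutive weeks. It treats all start weeks alike, although a rise caused by stopping a drug at the start would be expected early. Any end date leaves such a tail, and the follow-up visit and draw lie inside these weeks.

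None of this removes the on-drug versus off-drug pairing, or supplies a stated handover when the program ends.

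**Conclusion.** The point holds in a limited form. By design, drug-stoppers contribute an on-drug baseline and an off-drug follow-up value to a secondary outcome, and the analysis plan does not separate them. The visible text also states neither an end to the stop nor a handover at program end. That the high-glucose outreach lapses at week 16 is a further step, and it rests on the two weekly surveys being the same.

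The size is small: about 1 to 6 of 40 pairs under assumed shares of 2.5% to 15%. The documents give no basis for the direction or amount of the shift. It would be wrong to conclude that drug status at the final draw is wholly unrecorded, that participants are left without medical cover, or that the liver-fat result or its power is affected. This is a modest improvement worth considering, not a flaw in the main analysis. The judgement covers the visible text only, because Figure 1 is not shown.

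**What to change.** 1. **Analysis.** Report the insulin-resistance Wilcoxon comparison with and without participants whose glucose-lowering drugs differ between the two draws. Classify them from baseline drugs, the planned stop and the weekly drug-change reports, plus one dated current-drug question at the follow-up visit or draw. The question is not needed if Figure 1 or the visit form already contains it.
2. **Handover.** At program end, send each drug-stopper's primary care provider the last glucose reports, and the follow-up glucose and HbA1c results when available. The decision to restart stays with the treating physician.
3. **Optional.** Continue the weekly glucose, symptom and drug-change items for drug-stoppers until the final draw. This adds at most 4 short surveys each, or 4 × 1 = 4 to 4 × 6 = 24 in all under the assumed counts. Given the follow-up visit and draw in the same weeks, it gains little.

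Items 1 and 2 cost one extra analysis, one question for each of up to 40 people, and one template letter per drug-stopper. The reduced analysis would have slightly fewer pairs and should be read as a sensitivity check. The sample size, the primary analysis and the power statement do not change.
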